Recruitment Point 3. LDCT Result. After the patient has received the result, patients who have not previously enrolled or refused further contacts will be sent a short video recruitment message tailored to the result via a secure, encrypted email including a secure REDCap survey link, or a letter with a URL to a secure REDCap survey. It will invite them to join the study, and

give brief cessation advice from [name] or [name]. Patients will then be contacted by the RA who will use the same workflow as described for Point 1 (i.e., screen, consent, administer baseline survey). Patients who enrolled at an earlier point will receive a short video embedded in a secure REDCap survey tailored to their test result to address why quitting and study participation remain important.

Hispanic/Latino patients that do not enroll will have MRNs shared with study investigators to be approached for protocol # 2019P002549.

Patients may also be contacted for research purposes from the team in the future.

Recruitment Summary: Our recruitment strategy is designed to require little additional effort at busy radiology sites, but make systematic and repeated recruitment offers to enable us to achieve maximal reach.^{5,50,54,55,56,59} To provide data for our implementation evaluation (Aim 3), we will record the numbers and characteristics of patients who are identified, eligible, and enrolled at each time point. We will document reasons for ineligibility and refusal and document EHR-recorded sociodemographic and biological characteristics, medical history, and cancer history of refusers.

Randomization. Patients will be randomized at the time of enrollment (i.e., completed consent and baseline survey), stratified into 9 randomization strata (3 groups of LCS study sites and 3 recruitment points), to a LCS-tailored intervention treatment arm. The intervention arms will consist of 8 groups of equal proportions, based on a 3-factor fully crossed factorial design to efficiently test components that vary on counseling duration, NRT duration, and provision of systematic referral.

V. STUDY PROCEDURES

Data management. A centralized SQL database will be used for patient identification and recruitment, randomization, patient tracking, and data input. It will interface with all data collection efforts (RAs will enter in REDCap).

Intervention arm components

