Organizational Readiness. Site characteristics and site readiness will be measured at each study site. Employees will undergo local training and then each attending employee will answer the readiness items, identified by the SCALE collaboration. Data will be collected anonymously, and employees will be consented through a waiver of documented informed consent. Responses to these items will be collected at baseline and at the end of the intervention phase of the study.

Research staff may also use a Partners approved text messaging service to contact patients who have agreed to be sent text messages during the consent process. This will be used to maximize outcomes from study videos, follow up surveys, and study reminders.

The Area Deprivation Index (ADI) is a measure for social economical status. We plan on using ADI to control for social and economical factors that are not otherwise reported. We plan on using census.gov to import a csv file of participant addresses which will return the 2020 census block group for those addresses. Names and study details will not be included in the process. By knowing the census block group of an address, we can then link that address to the 2020 ADI score.

VI. BIOSTATISTICAL ANALYSIS

Assessment Plan

Outcomes

Primary smoking outcome: 7-day point-prevalence tobacco abstinence at 6-month follow-up.

Secondary smoking outcomes (1) self-reported 7-day abstinence at 3-, and 6- months follow-up; (2) significant reduction (>50% decrease from baseline in cigarettes/day⁸¹); and (3) >24-hour intentional quit attempt at 3-, and 6-months follow-up.

Measures

Moderators

Sociodemographic and biological characteristics [baseline only]. *EHR*: Sex, age, primary insurance, language preference for sessions and study materials. *Survey*: Race/ethnicity, education level, employment, and religiosity. Medical history [baseline and follow-up]. *EHR*: Comorbid tobacco-related disease, ambulatory visits, alcohol consumption. Screening result. *EHR*: Lung RADS score, results of any diagnostic tests (CT or biopsy). Smoking characteristics [baseline and follow-up]. *Survey*: Current cigarettes/day, number of years smoked, e-cigarette use, past and current use of cessation medication and other tobacco products, 24-hour intentional quit attempt, nicotine dependence (2-item Heaviness of Smoking Index from the Fagerström Test for Nicotine Dependence [FTND] which have predictive validity with the overall FTND^{82, 83}).

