Proximal Outcomes/Mediators

All proximal outcomes/mediators will be assessed via survey at baseline and follow-up. Smoking beliefs. Readiness to quit (1 item 10-point 'contemplation ladder' ^{84,85}), importance and confidence to quit (1 item 10-point scales), 4 item perceived lung cancer risk, and 2 item perceived benefits of quitting.^{47,57} Health and screening beliefs. Self-reported overall health status (1 item from the SF-36 survey⁸⁶), 2 item perceived benefits of screening.^{47,57} Emotional symptoms. Anxiety and depression symptoms (PROMIS Anxiety and Depression 4a short-forms), worry about lung cancer (1 item about level^{87, 88}). Environmental factors. Living with a smoker in the household, 1 item 4-point scale about rules about smoking in the household⁸⁹, environmental workplace/hobby exposure and social support (PROMIS emotional and informational 4a short forms).⁸⁸

Analysis plan

All analyses will be intent-to-treat; we will classify patients who are lost to follow-up and those who do not provide a sample as current smokers.⁹² We will explore whether the mechanism of missing data is missing at random by comparing patient characteristics between those who complete follow-up vs. those who do not. We will perform sensitivity analysis: 1) limited to those who have complete data, and 2) multiple imputation for missing data.⁹³

Factorial design

In a factorial research design, two or more independent variables are concurrently examined within the same trial.^{94, 95} The three proposed factors will be crossed with one another to create a total of eight experimental conditions. An equal number of subjects will be randomly assigned to each condition, using a random number generator. This is not an 8-arm randomized controlled trial, but instead allows for an efficient examination of main effects for each variable over the entire sample of 640 subjects. This approach allows examination of three key treatment development questions in a much more time-efficient and economical manner by simultaneously performing three studies within the single trial. This achieves power to detect between-group differences that is equivalent to performing three separate randomized trials.⁹⁴

Outcomes/analysis

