Outcome measures will be assessed at baseline, 3-, and 6-months follow-up. At the outset, we will examine the frequency distributions of all variables. Data from all PHS sites will be pooled for analysis, after confirming there is no significant heterogeneity among sites or adjusting as needed. We will compare the baseline characteristics to assess whether randomization distributed covariates evenly. We will determine whether there is differential dropout in the groups and consider developing probability-of-completion weights to obtain unbiased estimates of treatment effect. The primary analysis will assess the effects of each intervention component in terms of its association with the **primary outcome** (cotinine-confirmed or self report of cessation at 6-months follow-up), **secondary smoking outcomes** and **proximal outcomes/mediators**: (a) short vs long counseling (conditions 1/2/5/6 vs. 3/4/7/8), (b) short vs long NRT (conditions 1/3/5/7 vs conditions 2/4/6/8), and (c) provision of systematic referral or not (conditions 1-4 vs. 5-8). Given the balanced complete factorial design,⁹⁴ each of the three main effect estimates will be based on the full sample size of 640. Cross-sectional analyses will be conducted for outcomes assessed at 3, and 6 months separately. For binary outcomes, chi-square tests will be used to compare the outcomes between groups for each follow-up time. For continuous outcomes two-sample t-tests or Wilcoxon rank sum tests, whichever more appropriate, will be used to compare between groups. A longitudinal analysis using Generalized Estimating Equations (GEE) techniques will also assess the overall impact of each component by including data from all follow-up time points. The secondary analysis will examine the interaction between components, which will provide insight into whether certain combinations of components are most useful. We will test the three-way and two-way interaction terms in the regression models. If there are component interactions, we will determine whether the components are synergistic or antagonistic. Exploratory analyses will examine the moderator effects on treatment effectiveness of the intervention components and groups. Of primary interest are sociodemographic characteristics (sex, race/SES, age), smoking characteristics (quit motivation, nicotine dependence), medical history, LCS-related factors (test results, and point of study entry), delivery modality selected (phone vs. video) and language of participation (English vs. Spanish). We will test the effects of these factors in multivariable logistic regression models to determine their association with the primary and secondary smoking outcomes. We will test for interactions between intervention and these factors to determine whether

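### Continuous proximal outcomes are to be compared without their baseline values and with no rule for choosing the test; prespecified baseline adjustment would recover precision at no data cost

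*Combined protocol and SAP*

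**What the plan says.** All references are to the combined protocol and SAP.

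- **Test.** Section VI, Outcomes/analysis: "For continuous outcomes two-sample t-tests or Wilcoxon rank sum tests, whichever more appropriate, will be used to compare between groups". The same paragraph opens with "At the outset, we will examine the frequency distributions of all variables". It gives no criterion for preferring one test to the other.
- **Timing.** The same paragraph: "Cross-sectional analyses will be conducted for outcomes assessed at 3, and 6 months separately". No baseline covariate or change score is mentioned for these comparisons.
- **Longitudinal analysis.** A GEE analysis "will also assess the overall impact of each component by including data from all follow-up time points". It names no baseline covariate either.
- **Baseline data.** Section VI, Proximal Outcomes/Mediators: "All proximal outcomes/mediators will be assessed via survey at baseline and follow-up". Section IV, Randomization: "Patients will be randomized at the time of enrollment (i.e., completed consent and baseline survey"). The baseline survey therefore precedes allocation for every randomized patient.
- **Strata.** Section IV, Randomization: patients are "stratified into 9 randomization strata (3 groups of LCS study sites and 3 recruitment points"). Outcomes/analysis provides for site adjustment only if heterogeneity calls for it. Recruitment point appears there only as an exploratory moderator.
- **Which outcomes are continuous.** The primary outcome is abstinence. The listed secondary smoking outcomes are also binary; even cigarette consumption is dichotomized, as "significant reduction (>50% decrease from baseline in cigarettes/day"). The sentence on t-tests and Wilcoxon tests therefore governs chiefly the proximal outcomes and mediators. Outcomes/analysis does list these within the primary analysis of each component.

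**The concern.** The proximal measures (readiness, confidence, perceived risk, anxiety and depression symptoms, social support) are the constructs through which the counseling is meant to act. A patient's score at 3 or 6 months usually depends partly on the score at entry. A comparison of follow-up scores alone leaves that predictable variation in the error term, although the information needed to remove it is already collected.

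The open choice of test is a second gap. The t-test addresses a difference in means and the Wilcoxon test a shift in ranks. Until the choice is fixed, the quantity to be estimated is undefined for each scale, component and time point.

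At stake are the width of the confidence intervals for the proximal effects and the clarity of what is reported. The cessation result is not at stake.

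**Working it through.** **1. The plan's own figures.** The documents give no power or precision for any continuous outcome. The current figures for the binary primary outcome (section VI, Reduction from initial power calculations) were reproduced to fix the sample sizes and the sidedness of the test.

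- Inputs: 640 recruited; 559 followed at 3 months and 539 at 6 months; within-person correlation 0.6.
- Assessments per patient: (559 + 539)/640 = 1.716.
- Effective N = 1098/[1 + 0.716 × 0.6] = 768.2 (stated 768), or 384 per level.
- Two-sided 5% test of two proportions with pooled variance: 69.6% power for 10% vs 16% (stated 70%) and 81.1% for 10% vs 17% (stated 81%).
- A one-sided test would give 79.7% and 88.5%, so the plan's figures are two-sided.

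These figures do not depend on how continuous outcomes are analysed.

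**2. Unadjusted comparison of a continuous outcome at 6 months.**

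- Allocation to each component is 1:1, so 539/2 = 269.5 completers per level.
- Smallest difference detectable with 80% power, in SD units: (1.960 + 0.842) × √(2/269.5) = 2.80 × 0.0861 = 0.241.
- Power at a true difference of 0.20 SD: 64%.

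**3. The same comparison adjusted for baseline.** If ρ is the correlation between baseline and follow-up, the residual variance is multiplied by 1 − ρ². The detectable difference becomes 0.241 × √(1 − ρ²), and the 539 completers are worth 539/(1 − ρ²) unadjusted ones. The documents give no ρ for these scales, so the values below are assumed.

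| Assumed ρ | Variance factor | Detectable difference (SD) | Power at 0.20 SD | Equivalent unadjusted N |
|---|---|---|---|---|
| 0 (unadjusted) | 1.00 | 0.241 | 64% | 539 |
| 0.3 | 0.91 | 0.230 | 68% | 592 (+10%) |
| 0.5 | 0.75 | 0.209 | 76% | 719 (+33%) |
| 0.7 | 0.51 | 0.172 | 90% | 1057 (+96%) |

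A simulation with 269 per level (4,000 runs per ρ) gave power at 0.20 SD of 68%, 77% and 90% with adjustment, against 64% without.

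The 0.6 in Sample size/Power calculations must not be used as ρ. It describes binary cessation between 3 and 6 months, not a continuous scale between baseline and follow-up.

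**4. Covariate or change score.** A change score has variance factor 2(1 − ρ): 1.4, 1.0 and 0.6 at ρ = 0.3, 0.5 and 0.7. It loses precision below ρ = 0.5 and is less efficient than the covariate at all three values. The baseline should therefore enter as a covariate.

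**5. Choice of test.** Null simulations with 269 per level compared two ways of choosing.

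- Choice from the pooled distribution (skewness above 1, or a Shapiro test), with normal, gamma, lognormal and 10-point data: type I error 4.6% to 5.2%, no different from either test alone.
- Reporting whichever test is significant: 5.3% (10-point scale), 6.5% (normal) and 7.9% (lognormal).

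Only the second practice inflates error, and the plan does not describe it.

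**The case against.** The strongest reply is that nothing here is invalid. Under randomization the two-sample comparison is unbiased, and its standard error already reflects chance baseline imbalance. The outcomes concerned carry no power claim. Several are single-item or four-point scales, for which a rank test is defensible. The plan is also wider than one sentence: it adds the GEE analysis, regression models for component interactions, a check of baseline balance and conditional adjustment for site.

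Most of this stands. It limits the point to precision on proximal measures. It does not remove the gap, because none of those analyses names the outcome's baseline value, and the plan does not say what follows if the balance check finds a difference.

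A reader might draw two stronger conclusions, and the documents support neither.

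- *That the open choice of test gives two chances at significance.* The stated criterion is suitability, not the smaller p-value, and the plan does not say that distributions will be inspected by arm. Choice from the pooled distribution left the error rate near 5%. The fair criticism is a missing rule and an undefined estimand.
- *That leaving out the other two crossed factors does harm.* In a balanced factorial this causes no confounding and almost no loss. If each omitted factor had an effect of 0.20 SD (assumed), the outcome SD would rise by 1%: √(1 + 2 × 0.25 × 0.04) = 1.010.

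**Conclusion.** The point holds as a missed improvement in precision, together with an unspecified choice of test, for the continuous proximal outcomes and mediators. It is not an error of validity.

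The omission can be read directly from the text. The size of the gain cannot, because it rests on an assumed correlation. At 0.3 it is slight (0.241 to 0.230 SD); at 0.7 it is worth nearly twice the patients. The calculation also assumes 539 six-month completers split equally between the levels of each component, and a linear relation between baseline and follow-up.

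A reader might infer that the trial's power or its cessation result is in doubt. It is not: the primary and listed secondary smoking outcomes are binary and are analysed by other methods.

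**What to change.** In section VI, Outcomes/analysis, replace the sentence on continuous outcomes with a prespecified model:

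- For each continuous outcome, fit a linear regression at each follow-up, or the planned GEE across both, with the three component indicators, the outcome's own baseline value and the randomization strata (site group and recruitment point). Use robust standard errors.
- Report adjusted mean differences with confidence intervals.
- Name the Wilcoxon test as a sensitivity analysis. If a rank-based analysis is preferred as the main one for particular short ordinal items, list those items before the data are examined.
- State that the strata are included in every case, in place of site adjustment that depends on a heterogeneity check.

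The cost is SAP wording. The baseline survey is already a condition of randomization, so no new data, visits or patients are needed, and the baseline covariate uses one degree of freedom.

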Counseling delivery. Patients will be given a choice of phone-based or videoconferencing-based virtual visits; we will track patient choices. Telephone-based counseling is effective with other medical populations^{69, 70} and has been successfully used by Drs. [name], [name] and [name]. Technology use among seniors has rapidly increased over the past 5 years; smartphone use has quadrupled.⁷⁰ A videoconferencing option is innovative and feasible; over 67% of adults 65 years and older use the internet, almost half own a smartphone, and more than half have high-speed broadband at home.⁷² A patient account will be created and RAs will assist patients in videoconferencing setup.

(2) Nicotine Replacement Therapy (NRT) duration. The tobacco cessation counselor will promote medication use, describe all FDA-approved options, offer free NRT patches to smokers with no contraindication, and assist smokers who choose other medications to obtain prescriptions from their clinicians in the Partners System. Although use of medication will be promoted, it is not required for study participation. NRT dose will be determined by daily cigarette use: 21 mg/d patch for >10 cig/day, 14 mg/d patch <10 cig/day. Patients in the short duration arm will receive one 2-week kit. Patients in the long duration arm will receive one 4-week kit and are eligible for one additional 4-week refill, using a tapering dose schedule, for a total NRT duration of 8 weeks. The tobacco cessation counselor, in consultation with Drs. [name] or [name], will adjust the NRT dose to control withdrawal symptoms and minimize adverse effects. NRT will be mailed at no cost to patients. NRT has been safely distributed through quitlines in this way, and this approach was used safely in our recent work.⁵⁰ The tobacco cessation counselor will use a protocol to screen for NRT eligibility and discuss any eligibility questions or adverse effects with Drs. [name] or [name]. NRT kits will include instruction and patient information sheets in English or Spanish written for a 6th grade reading level. NRT can be initiated at any point during the 8 weeks of the trial and can start before a quit date, a newer treatment strategy that is associated with improved outcomes.⁶² Use of NRT will be supported during each tobacco cessation counseling call.

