
Sample size/ Power calculations

Power calculations are based on our primary analysis, which is to assess the effect of each intervention component (e.g., shorter counseling vs. longer counseling) on our primary outcome, 7-day point-prevalence tobacco abstinence at 6-month follow-up. This is a two-sample comparison between patients that receive one intervention component (e.g., longer counseling) and those that receive the other (e.g., shorter counseling). We conservatively estimate that 160 patients/month will have LCS, of whom 50% will be current smokers. Assuming a 50% enrollment rate, we aim to recruit a total N of 720 patients. This sample size allows us to allocate N=360 to each treatment component comparison (main effect). Our

Reference rate	Relative Risk		
	1.4	1.45	1.5
16%	0.71	0.80	0.87
17%	0.74	0.83	0.90
18%	0.77	0.86	0.92
19%	0.80	0.88	0.93
20%	0.83	0.90	0.95
21%	0.85	0.92	0.96
22%	0.87	0.93	0.97

outcome of interest will also be assessed at 3-month followup, which allows us to use a longitudinal generalized estimating equations approach wherein power is proportional to the within-person correlation. We estimate the correlation between 3 month and 6 month smoking cessation to be 0.6. Assuming N=360 patients in each condition, a Type 1 error rate of 0.05, a 25% attrition rate by 6 month follow-up, and a 15% cessation rate for the reference group, we will have 92.3% power to detect a risk ratio of 1.6 (15% vs. 21%). Under those same conditions, but with a 10% cessation rate for the reference group, we will have 79.0% power to detect a risk ratio of 1.6 (10% vs. 16%). Given that this is full factorial design, we will have the same power to detect two-way interactions between components. Further, we will also have 77.9% power to detect a risk ratio of 2.0 in the difference between our most intensive set of treatments (longer counseling, longer NRT, and community support; N=90) and our least intensive set of treatments (shorter counseling, shorter NRT, and no community support; N=90) after six months, assuming a 15% reference rate and 25% attrition.

Reduction from initial power calculations

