This study was initially powered conservatively to detect a smaller risk ratio of 1.4 and did not account for additional power provided through within-person correlation via repeated measurement of our outcome of interest. Initial power calculations, assuming a Type 1 error rate of 0.05, 25% attrition at 6 months, and no within-person correlation showed that our original N of 960 patients (N=480 per condition) gave us 85.0% power to detect a risk ratio of 1.4 with a reference rate of 15%. Updated power calculations accounting for within-person correlation of 0.6 show that this original N gives us 96.8% power to detect our target risk ratio of 1.6, assuming 25% attrition at 6 months and a 15% reference cessation rate.

Our previous power calculation assumed a 25% attrition rate at 6 months. We re-examined this assumption after halfway through the recruitment. Our new estimates are 12.7% attrition rate at 3 months and 15.9% attrition rate at 6 months. Based on these estimates, we further reduce the target recruitment from 720 to 640. Combining data from both 3-month (estimated N=559) and 6-month (estimated N=539) assessments, the effective sample size will be 768 after taking into account of within-person correlation using a conservative estimate of 0.6. The new sample size will have 70% power to detect a risk ratio of 1.6 (10% vs. 16%) and 81% power to detect a risk ratio of 1.7 (10% vs. 17%).

VII.. RISKS AND DISCOMFORTS (Stratify by common and uncommon)

Prior to enrollment, potential patients will be cautioned about the potential negative psychological and physical implications of joining the study and/or quitting smoking.

Psychological Risks

Individuals may find it stressful to answer questions and discuss their smoking behaviors. The risks associated with these discussions are minimal, especially when compared to the benefits of smoking cessation.

The potential risks to subjects include: 1) speaking with a counselor about smoking and/or cancer-related topics has the potential for increasing psychological vulnerability; 2) experiencing physical and emotional withdrawal symptoms from smoking cessation; and 3) potential side effects of using nicotine replacement therapy.

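### At N=640 the stated 70% and 81% power belong to an effect pooled over 3 and 6 months; power for the 6-month primary comparison is lower and is not given, and no rule says which analysis decides.

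*Combined protocol and SAP*

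**What the plan says.** All places are in the combined protocol and SAP.

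- **Section VI, Outcomes:** "Primary smoking outcome: 7-day point-prevalence tobacco abstinence at 6-month follow-up". Self-reported abstinence at 3 months is listed among the secondary outcomes.
- **Section VI, Sample size/ Power calculations:** "Power calculations are based on our primary analysis, which is to assess the effect of each intervention component", where the outcome is 6-month abstinence and the analysis is described as a two-sample comparison. The same paragraph then brings in the 3-month assessment, which "allows us to use a longitudinal generalized estimating equations approach", with an assumed within-person correlation of 0.6.
- **Section VI, Outcomes/analysis:** the two visits are analysed separately, and for binary outcomes "chi-square tests will be used to compare the outcomes between groups for each follow-up time". A GEE "will also assess the overall impact of each component by including data from all follow-up time points". No visit term, component-by-visit term, 6-month contrast or working correlation is stated.
- **Section VI, Reduction from initial power calculations:** "we further reduce the target recruitment from 720 to 640". From 559 patients at 3 months and 539 at 6 months, "the effective sample size will be 768 after taking into account of within-person correlation", giving 70% power for 10% vs 16% and 81% for 10% vs 17%.
- **Section VI, Analysis plan:** patients lost to follow-up are classified as smokers.
- **Section V, NRT duration:** the long arm may receive 8 weeks of patches and the short arm 2 weeks, and "NRT can be initiated at any point during the 8 weeks of the trial".

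**The concern.** The endpoint that defines success is at 6 months, but the only power quoted for the current sample size comes from an analysis that also uses 3-month abstinence. Pooling gains precision for the 6-month effect only if the component effect is the same at both visits. The plan neither states nor defends that assumption. In cessation treatment it is natural to ask whether an early difference fades.

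Two things are at stake. First, a reader of the sample size section would believe the primary comparison has 70% to 81% power when it has less. Second, the GEE and the 6-month chi-square can point in different directions. A significant overall effect driven by month 3 could then be presented as the component's result, because the plan does not say which analysis settles the primary question.

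**Working it through.** **Inputs.** From the reduction section: N=640, so 320 per factor level; attrition 12.7% and 15.9%; 559 and 539 expected at the two visits; correlation 0.6; rates 10% vs 16% and 10% vs 17%. From the power section: alpha 0.05. Its sidedness is not stated; two-sided reproduces the figures.

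**Step 1. Reproduce the stated power.** For n per level and difference d,

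power = Φ[(d − 1.96·s0)/s1], with s0 = √(2·p̄(1−p̄)/n) and s1 = √((p1(1−p1)+p2(1−p2))/n).

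With n = 768/2 = 384:
- 10% vs 16%: s0 = 0.02427, s1 = 0.02417; (0.06 − 0.04757)/0.02417 = 0.514, power **69.6%**.
- 10% vs 17%: s0 = 0.02466, s1 = 0.02453; (0.07 − 0.04834)/0.02453 = 0.883, power **81.1%**.

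These match the stated 70% and 81%, so the stated power is that of the pooled analysis. The 768 itself reproduces as the mean visit size times (2 − 0.6): 549 × 1.4 = 768.6. The usual formula for the mean of two correlated measures, 1098/1.6, gives 686, at which pooled power would be 64.7% and 76.6%. That is a separate matter, and nothing below depends on it.

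**Step 2. Power for 6 months alone at N=640.** Same formula.

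| Analysed at 6 months | n per level | 10% vs 16% | 10% vs 17% |
|---|---|---|---|
| Expected completers, 539 | 269.5 | (0.06 − 0.05678)/0.02886 = 0.112, **54.4%** | (0.07 − 0.05770)/0.02928 = 0.420, **66.3%** |
| All 640, missing = smoking | 320 | (0.06 − 0.05211)/0.02648 = 0.298, **61.7%** | (0.07 − 0.05295)/0.02687 = 0.634, **73.7%** |

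The second row assumes that the quoted rates already count missing patients as smokers. For scale, 80% power on 6 months alone needs 984 analysed patients (10% vs 16%) or 746 (10% vs 17%).

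**Step 3. How far the two analyses can part.** This is an illustration on assumed rates, because the documents give no visit-specific effects. Take 10% at both visits in the reference level, correlation 0.6, all 640 analysed, and a component effect d at 3 months only. A common-effect analysis on the risk-difference scale estimates d/2. Per level, the variance of the two-visit mean is ¼[v3 + v6 + 2(0.6)√(v3·v6)]/n, with v = p(1−p).

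For d = 7 points:
- reference: 0.072/320 = 0.000225
- component: 0.09158/320 = 0.000286
- SE = √0.000511 = 0.0226; 0.035/0.0226 = 1.548
- probability of significance = Φ(1.548 − 1.96) + Φ(−1.548 − 1.96) = **34%**

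The same steps give **11%** for 3 points (SE 0.0219) and **20%** for 5 points (SE 0.0223). With completers only (559/539) the three figures are 10%, 18% and 30%. Simulation of the 7-point case with 320 per level (linear GEE, robust variance) also gave 34%, while the 6-month chi-square stayed at 5%. In 32% of those trials a significant pooled benefit stood beside a non-significant 6-month test. With no effect at either visit the pooled test rejects in 5%.

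**Step 4. The NRT wording.** If patches may be started as late as week 8 and then used for 8 weeks, a long-arm patient could be on treatment until week 16, past a 3-month survey at about week 13; a short-arm patient starting then would finish at week 10. If the 8 weeks cover both start and use, both arms are off study patches by month 3. The text permits either reading.

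**The case against.** The plan keeps the 6-month endpoint in view. It is named as primary, it has its own chi-square test, and the GEE is introduced as an additional analysis. A null 6-month result would therefore be reported beside any pooled result. This stands, and the risk is one of interpretation and of an unstated deciding rule. A reader might infer that the sponsor intends to claim the primary outcome from the GEE; nothing in the documents says so.

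The common-effect model is also an inference, since no terms are written out. That stands too, although the reference to an overall impact and the calculation of a pooled effective sample both point to one effect across visits. A GEE with a component-by-visit term and a 6-month contrast would not have the problem.

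A reader might take the 11%, 20% and 34% as inflated type I error. They are not. A real 3-month effect exists in those scenarios, so the average effect is not zero and the pooled test is right to reject at those rates. It answers a different question. The scenarios also assume complete loss of effect by 6 months, which is the extreme case.

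Finally, a reader might conclude that long-arm patients will be on patch at the 3-month survey. That follows from only one reading of the wording, concerns one of three components, and comes with no estimate of how many patients start late.

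None of these replies touches the power gap in step 2.

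**Conclusion.** The point holds as a mismatch between the stated endpoint and the stated power, together with a missing decision rule. The 70% and 81% apply to an effect averaged over 3 and 6 months and assumed equal at each. For the 6-month comparison at N=640, power is about 54% to 62% for 10% vs 16% and 66% to 74% for 10% vs 17%; the range reflects whether completers or all 640 are analysed. These figures use the plan's own rates, attrition and alpha, taken as two-sided.

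The disagreement rates in step 3 rest on assumed visit-specific effects and show only what is possible. The documents support neither a claim of type I inflation nor a claim that the primary result will be taken from the GEE. The GEE remains the only analysis for which the current sample size has a stated power, so its role needs to be settled before the results are read.

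**What to change.** 1. State that the 6-month contrast decides the primary outcome for each component, either by the planned chi-square or by a GEE with visit and component-by-visit terms from which the 6-month contrast is taken. Name one of these.
2. Write out the GEE: terms, link, working correlation and variance estimator. Label any pooled effect as the average over 3 and 6 months, make it secondary, and report the 3-month contrast separately.
3. Restate power at N=640 for the 6-month comparison, say which analysis set it assumes, and keep the pooled power only as the power of the secondary analysis.
4. Reconcile the 8-week wording in the NRT section with the follow-up schedule, so that readers know whether study patches can still be in use at the 3-month survey.

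This is a change of SAP and protocol wording and needs no new data. The cost is a less favourable power statement: the 6-month contrast gains little from the 3-month data, and the plan would have to show power below the stated 70% and 81%.
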